## 1. SYNOPSIS

**COMPOUND:** Laryngeal mask versus no device in endoscopic retrograde cholangiopancreatography (ERCP) and endoscopic ultrasound procedures

STUDY No.: Seomask1

Anesthesiological management of ventilation with laryngeal mask in patients undergoing endoscopic retrograde cholangiopancreatography (ERCP) and endoscopic ultrasound procedures	
TRIAL LOCATION	P.I. Dott. xxx Department of Anesthesia and Intensive Care
STUDY OBJECTIVE(S)	Primary: Partial Pressure of Carbon Dioxide (PaCO 2 ) at the end of the endoscopic procedure  Secondary: 

- Number needing pressure support ventilation (PSV) in the treatment group

- pH, Partial Pressure of Oxygen (PaO2) at the end of the procedure

-Time to recover after the procedure

-Satisfaction of the procedure operator

-Satisfaction of the patient

STUDY DESIGN	Single Centre Comparative No profit 1:1 randomized Single blind (patient)
STUDY POPULATION Main selection criteria:	INCLUSION CRITERIA 

-age >18 years

-written informed consent

-elective ERCP and endoscopic ultrasound procedure

 EXCLUSION CRITERIA 

-pregnancy

-contraindication to propofol administration

-contraindication to mask insertion (e.g. malformation)

- emergency operation (not scheduled)

- preexisting causes of hypoventilation (e.g. chronic obstructive pulmonary disease, neuromuscular disease...)

Total expected number of patients:	60
INVESTIGATIONAL PRODUCT(S)	LMA ® Gastro ™ Cuff Pilot ™ The device allows the access to the esophagus with separation of the airways. The ventilation tube has an anatomical shape and a laryngeal mask (LMA) at the extremity. The cuff is adaptable to the pharyngeal shape with an open in front of the larynx. It has a parallel channel for the endoscope that ends under the cuff at the level of the upper esophageal sphincter (UES).
EFFICACY CRITERIA	Primary: Partial Pressure of Carbon Dioxide (PaCO 2 ) at the end of the endoscopic procedure

	
Secondary:
 
 
- Number needing pressure support ventilation (PSV) in the treatment group
 
- pH and PaO2 at the end of the procedure
 
-Time to recover after the procedure
 
-Satisfaction of the procedure operator
 
-Satisfaction of the patient
 
- Completion of the endoscopic procedure
 

SAFETY CRITERIA	No risk for the study subjects is expected
STUDY PROCEDURES	
Patients undergoing ERCP and endoscopic ultrasound will be screened the day before the procedure during the routine anaesthesiological visit. Eligible patients will be enrolled.
 
Immediately before the procedure patients will be allocated according to a simple randomization list to a treatment group and a control group. Patients will be blinded about the treatment, since they will be unconscious during the procedure (single blind study).
 
Patients in the control group will receive the standard anaesthesiological management of ERCP-patients, which is based on total intravenous anesthesia with propofol target controlled infusion (TCI) in spontaneous breathe without any airway devices.
 
In patients in the treatment group a laryngeal mask (LMA) specifically designed to permit gastrointestinal endoscopy will be inserted after the induction of sedation. This allows for expiratory end tidal CO2 (ETCO2) monitoring and assisted ventilation if needed.
 
In both groups anesthesia induction and maintenance will be performed according to a TCI protocol with a tailored site-effect target between 4 and 6 mcg/ml. Treatment group will receive PSV in case of ETCO2 raising above 50 mmHg. At the end of the endoscopic procedure an arterial gas analysis will be performed. Patients will be awakened as usual and then monitored in recovery room until full recovery. Data will be collected intraoperatively and during the recovery room stay.
 
The study will start after Ethical Committee approval.

STATISTICAL CONSIDERATIONS	
The PaCO2 in the treatment group is expected to be around 45 mmHg, due to the study design. A clinically significant hypoventilation is indicated by a PaCO2 around 50 mmHg and could be expected in the control group. We aim at observing such a 5 mmHg PaCO2 difference between groups with power 90% and alpha=0.05. PaCO2 SD during sedation is considered around 5 mmHg.
 
This yields a calculated 44 patients (22 per group).
 
We decide to enroll 60 patients (30 per group) taking into account dropouts and possible non-normality.
 
Continuous data will be reported as mean±SD[median(IQR)] and compared with the Student t tests on the equality of means or with the Wilcoxon rank-sum test (Mann-Whitney two-sample statistic) if not normal. Normality will be tested by visual inspection and with the Shapiro-Wilk W test for normality.
 
Categorical data will be reported as number(percentage) and compared with the Pearson's chi-squared test Fisher's exact test if appropriate.

DURATION OF STUDY PERIOD	6 months

**2. FLOW CHART**

	SCREENING PHASE (day -1)	TREATMENT PHASE (day 0)	RECOVERY ROOM PHASE (day 0)
Clinical Examination	X	X	X
Laboratory Testing (and pregnancy test)	X	X	
Inclusion/Exclusion Criteria	X	X	
Informed Consent	X		
Randomization		X	
Investigational Device Use		X	
AE /SAE recording (if any):		X	X

### 3. INTRODUCTION AND RATIONALE

Diagnostic and operative procedures of upper gastrointestinal (GI) tract are very common in all patients. The associated level of discomfort is extremely different and often subjective, but some procedures are difficult to tolerate because of long duration, prone position or significant stimulation of the upper airways. In case of obstructive jaundice suspicious for pancreatic lesion which needs cytopathologic determination, endoscopic retrograde cholangiopancreatography (ERCP) and endoscopic ultrasound are often performed at once. The endoscopic probe is conducted in duodenum, an endoscopic ultrasound and some biopsies are performed and then the biliary tract is investigated with a contrast agent injected from the papilla of Vater. Ducts dilatation or prosthesis placement can be performed if necessary. The more the complexity, the longer the procedure.

The procedure is generally performed with deep sedation. Many pharmacologic regimens are available and described in literature. Our institute adopts propofol target controlled infusion (TCI), setting a tailored target between 4 and 6 mcg/ml. This protocol usually guarantees unconsciousness and unresponsiveness of patients. Propofol is a handy intravenous hypnotic drug but the main adverse event is dose-related respiratory depression. Pre-existing reasons for hypoventilation can exacerbate this event. Specific categories prone to this condition are the elderly and the chronic obstructive pulmonary disease-patients. The possibility to ventilate the patient with a pressure support ventilation (PSV) is an interesting perspective. Laryngeal mask (LMA) is a useful tool when an invasive ventilation is not necessary and when neuromuscular block is not required.

This specific type of LMA allows to separate the gastric and respiratory tract and, allows the anesthesiologist to support patient's ventilation as (and only if) necessary.

### BACKGROUND and PRELIMINARY DATA

A review of 33.854 GI endoscopy in Scotland underlines that for upper GI endoscopy in ASA 3-5 patients, the participation of an anesthesiologist, particularly for airway management and sedation, is mandatory. Complications can occur during the procedure and the percentage of death is 0.059%.

A recent trial concerning the use of a gastro-laryngeal tube for airway management versus no devices found higher satisfaction, less degree of desaturation and faster recovery after anesthesia in the treatment group.

Another study regarding a novel method of positive pressure ventilation (mask adaptor) in upper GI procedures reported an incidence of 3/30 (10%) carbon dioxide end-tidal (ETCO2) > 50 mmHg. This value exceeds the normal range of 35-45 mmHg and has several physiological implications (e.g. cerebral vasodilatation, tachycardia, lethargy)

### ORIGINALITY OF THE PROPOSAL

Patients in spontaneous breathe without airway devices could reach a high level of carbon dioxide (CO2) totally unknown to the anesthesiologist which has no tool to measure it. The introduction of a LMA in upper GI procedures could improve not only the monitoring but also the management of these patients. Literature has very few examples of airway management during GI procedures. Nowadays, new devices have been patented and are currently used in anesthesia. Our proposal is to introduce LMA in GI endoscopy to improve patient and clinicians satisfaction, reduce procedure-related complications and shorten recovery after anesthesia.

### MAIN EXPECTED RESULTS AND IMPACT

This randomized controlled trial aims to demonstrate a beneficial effect of LMA in GI endoscopic procedure. In details we hypothesize:

- a faster recovery because of maintenance of normal level of CO2.
- a higher satisfaction for patient, anesthesiologist and endoscopic operator because of deep level of sedation also in more fragile population
- an increased safety for all patients and in particular in the specific population at significant risk for hypoventilation

The results of this study can support the use of LMA in all ERCP and/or GI endoscopic procedures also in other centers.

#### **4. STUDY OBJECTIVES**

##### **4.1 Primary**

Partial Pressure of Carbon Dioxide (PaCO2) at the end of the endoscopic procedure

##### **4.2 Secondary**

Secondary endpoints will be:

- Number needing pressure support ventilation (PSV) in the treatment group
- pH and PaO2 at the end of the procedure
- Time to recover after the procedure
- Satisfaction of the endoscopy operator
- Satisfaction of the patient

#### **5. STUDY DESIGN**

##### **5.1 Description of the protocol**

This is a monocentric randomized controlled trial of superiority of LMA use in GI endoscopic procedures. Randomization is centralized. The study is single blind (patient). The study is no-profit.

##### **5.2 Duration of study**

Every patients undergoing scheduled ERCP and endoscopic ultrasound will be screened and consecutive eligible patients will be enrolled. The study starts after randomization and ends after discharge from the recovery room.

#### **6. SELECTION OF PATIENTS**

##### **6.1 Number of patients planned : 60**

##### **6.2 Inclusion criteria**

- age  $\geq$ 18 years
- written informed consent
- elective ERCP and endoscopic ultrasound procedures

6.3 Exclusion criteria

- pregnancy
- emergency procedure
- contraindication to propofol administration
- contraindication to mask insertion (e.g. malformation)
- preexisting causes of hypoventilation (e.g. chronic obstructive pulmonary disease, neuromuscular disease...)

#### **7. TREATMENTS**

##### **7.1 Investigational Medicinal Product (IMP)**

All patients in both groups will receive propofol TCI with a tailored target between 4 and 6 mcg/ml until the end of the procedure.

The treatment group will also receive LMA insertion after induction of anesthesia and ETCO2 monitoring. In case of hypoventilation with an ETCO2 higher than 50 mmHg the patient will receive PSV to normalize this value.

Both group will receive a laboratory testing (peripheral arterial sample) at the end of the procedure, when the patient is still sedated, to obtain important data about ventilation.

##### **7.2 Other products**

Intraoperatively, there will not be any limitation to the use of any drugs as in general practice.

##### **7.3 Description of blinding methods.**

All the patients will be blinded to treatment assignment for the duration of the study. This study is single blind.

##### **7.4 Method of assigning patients to treatment group (if applicable)**

Randomization will be performed centrally by a simple randomization list.

#### 7.5 Responsibilities

There is no specific drug under investigation.

#### 7.6 IMP accountability and compliance

There is no drug company involved and there is no specific drug under investigation.

### 8. STUDY PROCEDURES

Subjects will be allocated according to a simple randomization list. Data will be collected by the investigators or trained colleagues.

After periferal venous catheter insertion and vital parameters monitoring, patients will receive propofol TCI with a tailored target between 4 and 6 mcg/ml. The treatment group will receive LMA insertion and ETCO2 monitoring throughout the procedure. In case of hypoventilation, with an ETCO2 above 50 mmHg, the patient will be supported as necessary with PSV. The control group will not receive any airway device, according to the standard treatment. At the end of the procedure, both group will receive a laboratory testing (periferal arterial sample), when the patient is still sedated. Vital parameters monitoring will continue in recovery room. Patients will be discharge as usual with an Aldrete score > 9.

Data will be collected during the procedure and in recovery room.

Data will be stored in electronic database without mention to patient's name.

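### Time to recover has no masked assessor and no defined clock or checking interval, so this secondary endpoint is open to assessor bias towards the mask

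*Combined protocol and SAP*

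**What the plan says.** **Who is blinded.** Section 7.3 reads: "All the patients will be blinded to treatment assignment for the duration of the study. This study is single blind". The Synopsis explains why: "Patients will be blinded about the treatment, since they will be unconscious during the procedure (single blind study". Section 5.1 also limits the blind to the patient. No section names a blinded assessor.

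**Who collects the data.** Section 8: "Data will be collected by the investigators or trained colleagues". The same section places collection both in the procedure and in the recovery room, and does not say whether recovery-room collectors know the arm.

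**How recovery is judged.** Section 8.1 lists time to recover after the procedure as a secondary endpoint and adds nothing to the name. The nearest criterion is the discharge rule in section 8: "Patients will be discharge as usual with an Aldrete score > 9". The Synopsis gives the order of events: "Patients will be awakened as usual and then monitored in recovery room until full recovery".

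**Satisfaction.** Operator and patient satisfaction are both secondary endpoints. Neither has a stated scale, time point or method of collection.

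**What is expected.** Main Expected Results and Impact opens its list of hypotheses with "a faster recovery because of maintenance of normal level of" CO2, followed by higher satisfaction. Originality of the Proposal gives shorter recovery as one purpose of introducing the device.

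**The concern.** Four features meet on one endpoint: a threshold that depends on an observer's rating, a clock with no stated ends, no masking of the person who rates, and a declared expected direction. An assessor who knows the arm can influence when the patient is scored, how often, and whether a borderline score counts as meeting the threshold. None of this needs bad faith.

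The missing clock is a related weakness. Awakening comes before recovery-room monitoring, and in one arm a device must also be removed. The protocol does not say where removal takes place. If it happens before arrival, timing from recovery-room entry would omit a step that differs between arms, even with a perfectly masked scorer.

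At stake is the interpretation of a positive recovery result. Unlike the endoscopist, who cannot be blinded, a recovery-room scorer could be: the mask is used during the procedure, so nothing visible in the recovery room need reveal the arm if it is removed before arrival.

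**Working it through.** **1. What the documents settle and what they leave open**

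| Item | Stated | Not stated |
|---|---|---|
| Blinding (Synopsis, 5.1, 7.3) | Patient only | Any masking of assessors |
| Collectors (8) | Investigators or trained colleagues, in both settings | Whether the same person covers both; whether they know the arm in recovery |
| Time to recover (4.2, 8.1) | Name only | Start, stop, assessor, checking interval |
| Aldrete > 9 (8) | Discharge criterion | Link to time to recover; who scores it |
| Patient satisfaction (4.2, 8.1) | Satisfaction of the patient, who is blinded | Scale, timing, who asks or records |
| Operator satisfaction (4.2, 8.1) | Satisfaction of the endoscopy operator, who is not blinded | Scale, timing |

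**2. The plan's own figure**

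Section 11.1 gives a difference of 5 mmHg, SD 5 mmHg, power 90% and alpha 0.05. The normal approximation is n per group = 2 × (1.960 + 1.282)² × (5/5)² = 21.01, rounded up to 22, or 44 in total. This reproduces the stated figure. The exact t test solves to 22.02 per group, with power 0.8997 at 22. A one-sided test would give 18 per group, so the plan's test is two-sided. This concerns PaCO2 only and is unaffected by the present point.

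**3. Illustration for time to recover**

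Inputs: 30 per arm (section 11.1), two-sided 5% Student t test (section 11.2, with sidedness from step 2), no true difference. The bias b, in SD units, is an assumption; the documents give no value.

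Degrees of freedom = 60 − 2 = 58; critical value 2.002; noncentrality = b / √(2/30) = b × √15 = 3.873b. The rejection probability is the two-tailed noncentral t probability beyond ±2.002.

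| Assumed bias (SD) | Noncentrality | Chance of a significant result with no true effect |
|---|---|---|
| 0 | 0 | 0.050 |
| 0.1 | 0.387 | 0.067 |
| 0.25 | 0.968 | 0.159 |
| 0.5 | 1.936 | 0.478 |

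**4. Sensitivity to dropout**

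If only 22 per arm were evaluable (df = 42, noncentrality = b / √(2/22) = 3.317b), the same biases give 0.062, 0.128 and 0.367. The inflation is smaller but has the same pattern.

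**5. Scale in minutes**

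The documents give no SD for recovery time. If it were 10 minutes (assumption), 0.25 SD is 2.5 minutes and 0.5 SD is 5 minutes.

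**The case against.** The strongest reply is that much of the worry rests on silence. The sentence on data collection is general. It does not say that one person collects in both rooms, or that recovery-room collectors know the arm. Aldrete > 9 is a discharge rule and is not expressly tied to the endpoint. No section starts the clock at recovery-room entry, and the endpoint's name points to the end of the procedure. Section 13.2 mentions an attached printed case report form, not available here, which may hold time fields and a satisfaction scale. The inflation table would fit any unmasked continuous outcome at this sample size, and section 11.2 would replace the t test with the Wilcoxon test if the data were not normal.

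All of that is fair. It limits the point to an exposure that the plan leaves open; it does not show that bias will occur. The exposure remains, because a reader can rely on assessor masking only if the protocol states it, and the section on blinding names the patient alone.

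A reader might also infer that arm-aware investigators score patient satisfaction. The documents do not support this. The endpoint is listed as the patient's own satisfaction, and the patient is the one blinded party: "All the patients will be blinded to treatment assignment for the duration of the study". The remaining exposure is an arm-aware person asking the question or recording the answer. The subjective outcome certain to be rated unblinded is operator satisfaction.

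Finally, masking must not restrict what clinical staff are told about a patient just out of deep sedation. That stands, and the change proposed here leaves handover alone.

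**Conclusion.** The point holds for time to recover. Followed as written, the plan allows this endpoint to be assessed by someone who knows the arm, against a staff-rated threshold, on an undefined clock and at unspecified intervals, with the favoured direction already declared.

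It is a secondary endpoint. The primary endpoint is a laboratory measurement and the sample size is unaffected, so it would be wrong to infer that the main comparison is compromised. Nor do the documents show that recovery-room assessors will know the arm, or that they are the people who were in the procedure room; they only fail to prevent it.

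The rates of about 7%, 16% and 48% are correct for their inputs. They rest on assumed biases, 30 evaluable patients per arm and a t test, apply to time to recover only, and are not estimates of the bias in this trial. This is worth correcting before enrolment because the correction is cheap.

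**What to change.** Add to sections 7.3 and 8:

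1. In both arms, the Aldrete score used for the endpoint is recorded by existing recovery-room staff who were not in the procedure room and are not told the allocation by the study team. Clinical handover stays unchanged. The form records whether the scorer knew the arm.
2. The endpoint score is taken at the same fixed interval in both arms.
3. Time to recover runs from the end of the endoscopic procedure (endoscope withdrawal) to the first score meeting the protocol's own threshold. Awakening and, where it applies, mask removal then fall inside the interval in both arms. Discharge practice is not altered.
4. Patient satisfaction is completed by the patient, with the scale and time point stated. Operator satisfaction is reported as open-label.

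The cost is protocol wording, one field on the case report form and a short instruction to recovery-room staff. No extra staff or visits should be needed, assuming these staff already score patients for discharge; the protocol describes discharge on this score as usual practice but does not name the scorer. The downside is that some unmasking will occur, and its frequency must be reported by arm.

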#### 8.1 Efficacy

The primary endpoint of the study will be the PaCO2 at the end of the endoscopic procedure.

Secondary endpoints will be:

- Number needing pressure support ventilation (PSV) in the treatment group
- pH and PaO2 at the end of the procedure
- Time to recover after the procedure
- Satisfaction of the procedure operator
- Satisfaction of the patient
- Completion of the endoscopic procedure

### 9. PATIENT SAFETY

No risk for the study subjects is expected.

### 10. TEMPORARY OR DEFINITIVE TREATMENT DISCONTINUATION

Does not apply.

### 11. STATISTICAL CONSIDERATIONS

#### 11.1 Determination of sample size

The PaCO2 in the treatment group is expected to be around 45 mmHg, due to the study design. A clinically significant hypoventilation is indicated by a PaCO2 around 50 mmHg and could be expected in the control group. We aim at observing such a 5 mmHg PaCO2 difference between groups with power 90% and alpha=0.05. PaCO2 SD during sedation is considered around 5 mmHg (Yamakage M, Kamada Y, Toriyabe M, Honma Y, Namiki A. Changes in respiratory pattern and arterial blood gases during sedation with propofol or midazolam in spinal anesthesia. J Clin Anesth 1999; 11:375–9).

This yields a calculated 44 patients (22 per group).

We decide to enroll 60 patients (30 per group) taking into account dropouts and possible non-normality.

#### 11.2 Statistical Methods

All data will be analyzed according to the intention-to-treat principle, beginning immediately after randomization. Data will be stored electronically and analyzed by use of the R software ( R Development Core Team (2008). R: A language and environment for statistical computing. R Foundation for Statistical Computing, Vienna, Austria. ISBN 3-900051-07-0, URL <http://www.R-project.org.>).

All data analysis will be carried out according to a pre-established analysis plan.

Continuous data will be reported as mean±SD[median(IQR)] and compared with the Student t tests on the equality of means or with the Wilcoxon rank-sum test (Mann-Whitney two-sample statistic) if not normal. Normality will be tested by visual inspection and with the Shapiro-Wilk W test for normality. Categorical data will be reported as number(percentage) and compared with the Pearson's chi-squared test Fisher's exact test if appropriate.

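### Naming Welch's t test instead of Student's for PaCO2 is a free improvement: CO2-triggered support in one arm and a simple allocation list mean that SDs and arm sizes may both differ

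*Combined protocol and SAP*

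**What the plan says.** - **Test.** Section 11.2 (repeated in the synopsis) has continuous data "compared with the Student t tests on the equality of means", or with the Wilcoxon rank-sum test when normality fails. Neither place mentions unequal variances, a variance check or Welch's test.
- **LMA arm.** Section 7.1 provides that in hypoventilation with an end-tidal CO2 "higher than 50 mmHg the patient will receive PSV to normalize this value".
- **Control arm.** Section 8: "The control group will not receive any airway device, according to the standard treatment". No CO2-triggered support is described for controls. The section on originality in the introduction says that the anaesthetist has no means of measuring CO2 in patients without a device.
- **Allocation.** Section 7.4: "Randomization will be performed centrally by a simple randomization list". No blocking is described. Section 11.1 intends 30 per group and expects dropouts, without giving a rate.
- **Planning SD.** Section 11.1: "SD during sedation is considered around 5 mmHg". This one value serves both arms.

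**The concern.** Student's test estimates one common variance and applies it to both arms. Here the intervention acts on the upper end of the outcome distribution in one arm only, so the LMA arm may well have the smaller spread. If the arms also differ in size, the pooled standard error is too small when the more variable arm (controls) is the smaller one, and too large when it is the larger one. The primary p value is then somewhat too liberal or too conservative, depending on the split that the list happens to produce. The Wilcoxon fallback does not address this, because non-normality triggers it and unequal spread does not.

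**Working it through.** **1. The plan's own figure.** Inputs from section 11.1: difference 5 mmHg, SD 5 mmHg, power 90%, alpha 0.05 (sidedness not stated).

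n per arm = 2(z₀.₉₇₅ + z₀.₉₀)² × SD²/δ² = 2(1.960 + 1.282)² × 25/25 = 21.0, rounded up to 22.

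This matches "This yields a calculated 44 patients (22 per group"). The exact t calculation gives 22.02 per arm (power 89.97% at 22). A one-sided test would give 18, so two-sided is meant.

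**2. How different could the SDs be?** The documents give no SD by arm, so this step is assumption. Take spontaneous PaCO2 as N(50, 5), as planned for controls. In the LMA arm, replace values whose end-tidal CO2 exceeds 50 by a post-support value with mean 40–45 and SD 2–2.5, with a PaCO2–ETCO2 gap of 0–5 mmHg. The LMA-arm SD comes out at roughly 2.8–4 mmHg, and at 2.6–4.1 at the extremes of these assumptions.

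**3. How unequal could the arms be?** Treat the simple list as 60 independent 1:1 allocations, X ~ Binomial(60, 0.5):
- exactly 30:30: 10%
- 34:26 or worse: 37%, of which half (18%) has the LMA arm larger
- 35:25 or worse: 25%, of which half (12%) has the LMA arm larger

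**4. Why both conditions are needed.** Take SDs of 3 (LMA) and 5 (control), and compare the true variance of the mean difference with the variance that Student's test expects.
- *35 LMA:25 control.* True: 9/35 + 25/25 = 1.257. Pooled: (34×9 + 24×25)/58 = 15.62, times (1/35 + 1/25) = 1.071. Ratio of true to assumed SE = √(1.257/1.071) = 1.08, so liberal.
- *25 LMA:35 control.* True: 9/25 + 25/35 = 1.074. Pooled: (24×9 + 34×25)/58 = 18.38, times 0.0686 = 1.260. Ratio 0.92, so conservative.
- *30:30.* True: 9/30 + 25/30 = 1.133. Pooled: 17 × 2/30 = 1.133. Ratio 1.00.

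**5. Size of the nominal 5% two-sided Student test.** Simulated normal data with equal means and control SD 5; repeat runs differ by about 0.1–0.2 percentage points.

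| LMA SD | 30:30 | 35 LMA:25 control | 25 LMA:35 control | averaged over random splits |
|---|---|---|---|---|
| 5 | 5.0% | 5.0% | 5.0% | 5.0% |
| 4.1 | 5.0% | 5.9% | 4.3% | 5.1% |
| 3 | 5.1% | 7.2% | 3.5% | 5.2% |
| 2.6 | 5.1% | 7.8% | 3.3% | 5.3% |

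Welch's test was between 4.8% and 5.2% in every setting.

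**6. Does the fallback help?** The full Student/Wilcoxon rule with a Shapiro–Wilk gate was simulated at SDs of 3 and 7, a wider contrast than the plan's figures suggest and used only for illustration. It gave 9.3% at 36 LMA:24 control and 2.8% at 24:36, so it does not repair the problem.

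**7. Cost in power.** For 5 mmHg, SD 5 in both arms and 30 per arm, power is about 97% with either test (96.8% for Student, 96.7–96.8% for Welch).

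**The case against.** The case for leaving the plan alone has several sound parts.

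- **Unequal SDs are inferred.** The plan states one SD, and support is triggered by end-tidal CO2, so it is not a hard cap on PaCO2. This stands; the SD range above is an assumption. At its upper end (4.1 against 5) the distortion is under one percentage point at 35:25.
- **The null is somewhat artificial.** The mechanism that narrows the LMA arm also lowers its mean. If support had no effect and the arms were otherwise alike, the two distributions would be the same and Student's test would be valid. Equal means with unequal SDs needs some effect that offsets the support. This also stands, and it limits the weight of the figures in step 5.
- **The average error is close to nominal.** Before randomisation Student's size is 5.1–5.3%. This is correct. The departure is conditional on the split obtained, but that split is the one on which the reported p value rests.
- **The arms are meant to be 30 each.** That is the intention in section 11.1, but a simple list does not enforce it, and dropouts can unbalance the arms further.

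A reader might infer that the error rate is wrong whenever the arms end up unequal. It is not: unequal sizes with equal SDs leave 5%, and unequal SDs at 30:30 leave about 5.0–5.1%. A reader might also apply the point to a confidence interval. The documents plan none for the PaCO2 difference, only descriptive summaries and a test.

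**Conclusion.** The point holds as a free improvement to the primary test. It does not show that the planned test is invalid or that the trial's overall type I error is materially inflated. Unequal spread is plausible by design and unequal arm sizes are likely under a simple list. When both occur, Student's size moves to about 5.9–7.8% in one direction or 3.3–4.3% in the other at a 35:25 split, while Welch's stays near 5%. These figures rest on normal data, equal means, a control SD of 5, LMA SDs of 2.6–4.1 from assumed post-support values and an assumed PaCO2–ETCO2 gap of 0–5 mmHg, and independent 1:1 allocation. The liberal direction, at 35:25 or worse, arises in about 12% of lists. The sample size is not in question: 22 per group is reproduced.

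**What to change.** In section 11.2 and the synopsis, replace the Student t test with the Welch (unequal-variance) t test for PaCO2 and the other continuous endpoints. In R, which the plan already names, this is the default of the t test function (var.equal = FALSE). Make the change before any outcome data are seen, so that the choice does not depend on the observed SDs or split.

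The cost is one phrase in two places. It needs no more patients or data and loses no material power at the planned SD. Where Student's test is liberal, Welch's will reject less often, but this corrects the error rate and is not a loss of efficiency.

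### The primary PaCO2 comparison is valid but leaves age unused, although age is the one named risk factor for hypoventilation still enrolled; prespecifying it as a covariate is a small, cheap improvement.

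*Combined protocol and SAP*

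**What the plan says.** - **Analysis.** Section 11.2 (repeated in the Synopsis, Statistical considerations) has continuous data "compared with the Student t tests on the equality of means or with the Wilcoxon rank-sum test", the latter if the data are not normal. No covariate, adjusted analysis or sensitivity analysis is described. Section 11.2 also refers to a pre-established analysis plan, which is not reproduced separately.
- **Risk factors.** Section 3 states: "Specific categories prone to this condition are the elderly and the chronic obstructive pulmonary disease-patients". The condition meant is respiratory depression under propofol, which is the mechanism behind the primary endpoint.
- **Eligibility.** Section 6.3 excludes "preexisting causes of hypoventilation (e.g. chronic obstructive pulmonary disease, neuromuscular disease" and similar conditions. Section 6.2 sets a lower age limit and no upper one.
- **Allocation.** Section 7.4: "Randomization will be performed centrally by a simple randomization list". The Synopsis and Section 8 agree. No stratification is mentioned.
- **Size.** Section 11.1 derives 44 patients from a 5 mmHg difference and an SD of 5 mmHg, then states: "We decide to enroll 60 patients (30 per group) taking into account dropouts and possible non-normality".

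**The concern.** The protocol names two patient characteristics that drive the mechanism it measures. It removes one by exclusion and uses the other in neither the randomization nor the analysis. With about 30 patients per arm and no stratification, the arms can differ in age by chance, and nothing planned would correct for that.

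Two things are at stake. The first is precision: if age explains part of the variation in PaCO2, an unadjusted comparison leaves that part in the error term. The second is interpretation. If the arms turn out to differ in age, a reader can cite Section 3 against the result, and any adjustment made at that stage would be post hoc.

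**Working it through.** **Inputs from the documents (Section 11.1).** Difference 5 mmHg, SD 5 mmHg, alpha 0.05, power 90%, 30 per arm planned. Sidedness is not stated; two-sided is assumed.

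**Inputs assumed.** Within-arm age-PaCO2 correlation r = 0.2 to 0.4, the same in both arms; equal arms of 30; all 60 patients analysed.

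**1. The plan's own figure.** n per arm = 2 × (1.960 + 1.282)² × 5² / 5² = 21.01, rounded up to 22, so 44 in total. This matches Section 11.1. A one-sided 0.05 test would give 18 per arm, so the two-sided reading fits. By the noncentral t distribution, power is 89.97% at 22 per arm and 96.8% at 30 per arm.

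**2. Precision without adjustment.** SE = 5 × √(2/30) = 1.291 mmHg. Half-width of the 95% CI = 2.002 × 1.291 = 2.58 mmHg.

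**3. Precision with age in the model.** Residual SD = 5 × √(1 − r²). Fitting one covariate at N = 60 multiplies the variance by 1 + 1/56 on average and leaves 57 degrees of freedom instead of 58.

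| r | Variance ratio, (1 − r²) × 57/56 | Half-width (mmHg) | Power at 5 mmHg |
|---|---|---|---|
| unadjusted | 1 | 2.58 | 96.8% |
| 0 | 1.018 | 2.61 | 96.5% |
| 0.1 | 1.008 | 2.60 | 96.7% |
| 0.2 | 0.977 | 2.56 | 97.1% |
| 0.3 | 0.926 | 2.49 | 97.7% |
| 0.4 | 0.855 | 2.39 | 98.5% |

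Break-even: (1 − r²) × 57/56 = 1 gives r = √(1/57) = 0.13. Simulation of 20,000 trials per setting under simple randomization agrees: power goes from about 96.5% unadjusted to about 97%, 97.5% and 98% at r = 0.2, 0.3 and 0.4.

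**4. Cost if age is irrelevant (r = 0).** At 5 mmHg, power falls from 96.8% to 96.5%, a loss of 0.3 points. At an assumed true difference of 4 mmHg the same formula gives 86.1% against 85.5%, a loss of 0.6 points.

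**5. Chance imbalance.** The standardized age difference between arms has SD √(2/30) = 0.258. The probability that it exceeds 0.5 in either direction is 2 × [1 − Φ(0.5/0.258)] = 5.3%. The resulting shift in the unadjusted difference is r × 5 × 0.5.

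| r | Shift at 0.5 SD (mmHg) | Share of 5 mmHg | Type I error given that imbalance | Power if the imbalance is adverse |
|---|---|---|---|---|
| 0.2 | 0.50 | 10% | 6.3% | 94% |
| 0.3 | 0.75 | 15% | 7.8% | 92% |
| 0.4 | 1.00 | 20% | 9.9% | 89% |

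The last two columns use a normal approximation with mean shifted by the amount shown and conditional SE 1.291 × √(1 − r²). For r = 0.4 the conditional SE is 1.183, so the type I error is P(Z > (2.530 − 1.0)/1.183) + P(Z < (−2.530 − 1.0)/1.183) = 0.098 + 0.001. Averaged over all randomizations, the type I error stays at 5%.

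**The case against.** The strongest reply is that nothing here is an error. An unadjusted two-sample comparison of a randomized endpoint is valid, and choosing a t test over a covariate-adjusted model in a 60-patient trial is a preference. That stands, and it rules out two stronger readings. A reader might infer that the primary analysis is biased or that its alpha is inflated. It is not: an age imbalance favours either arm equally often, and the raised error rates above apply only given a particular imbalance. A reader might also infer that precision is certainly lost. The documents give no age-PaCO2 correlation, so that cannot be shown.

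The design also gives reasons to expect a weak correlation. The propofol target is tailored in both arms, so dosing may already reflect sensitivity. Pressure support is triggered by ETCO2 in the mask arm only, which limits PaCO2 there. Other causes of hypoventilation are excluded. If the correlation in the mask arm is half that in the control arm, simulated gains at 5 mmHg fall to about 0.1, 0.6 and 0.9 points for r = 0.2, 0.3 and 0.4.

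Larger gains can be quoted by assuming a 4 mmHg difference (about 85% rising to 86%, 88% and 89–91%), but the plan's target is 5 mmHg. The choice of standard error matters too: HC3 errors cost roughly a further 0.3 to 1 point and remove the gain at r = 0.2, whereas HC1 behaves like the model-based error.

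Finally, that age is recorded is an inference from its being an eligibility criterion, since no list of CRF variables is visible. The separate analysis plan might already adjust for age. What survives is the prespecification argument: the cost is small, and the protocol itself supplies the reason to look at age.

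**Conclusion.** The point holds as a minor refinement. The planned test is valid. It leaves unused the only risk factor named in Section 3 that remains in the trial population, and the randomization does not balance that factor.

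On the plan's own inputs the average gain is small: about 0 to 2 power points from about 97%, and at most about 0.2 mmHg off the CI half-width (2.58 to 2.39), for r between 0.2 and 0.4. There is no net gain below r of about 0.13. The better reason to act is protection, fixed in advance, against a chance age imbalance. One of 0.5 SD or more occurs in about 5% of such trials, and at 0.5 SD the estimate shifts by 0.5 to 1.0 mmHg, still well inside the half-width of 2.58 mmHg.

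These figures rest on the assumed r, a common slope in both arms, an SD of 5 mmHg and all 60 patients analysed. The gain would matter more if the SD were larger: at an assumed SD of 7 mmHg, power is 77.7% unadjusted and 80.7% adjusted at r = 0.3.

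**What to change.** In Section 11.2, and to match in the Synopsis:

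- Define the primary analysis as a linear model of end-of-procedure PaCO2 on randomized arm and age as a continuous covariate.
- State the standard error in advance, either model-based or HC1.
- Report the adjusted mean difference with its 95% CI.
- Keep the planned unadjusted t/Wilcoxon comparison as a supportive analysis, which retains the provision for non-normal data.
- Do not add procedure length as a covariate, because it arises after randomization.
- Confirm that age is a CRF field. If the separate analysis plan already adjusts for age, say so in 11.2.

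The cost is a sentence or two of text, one degree of freedom out of 58, and about 0.3 to 0.6 power points if age is unrelated to PaCO2. No new data should be needed, provided age is recorded as eligibility implies.
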